Treatment assignment	Randomization: Eligible individuals are randomly assigned to receive influenza vaccination with a randomly chosen vaccine brand or no vaccination 1:1	Matching: Eligible individuals who are vaccinated in each country during the study period will be matched 1:1 with individuals who have not yet received a vaccine by age (5-yr bins), sex, region of residence, and presence of comorbidities. Unvaccinated individuals are assigned the index date (date of vaccination) of the matched vaccine recipient.
Outcomes	
Primary:
 
 • Hosp. due to Influenza – Lab. conf + J09-J11 • Lab. conf. Influenza A and B (combined and separately) • Death with influenza – Lab. conf within 30 days before date of death 
Secondary:
 
 • Hosp. due to ILI – J09-J11 • Hosp. due to ARI or SARI – J09-J22 • Hosp. due to Influenza with ICU admission • All-cause mortality 	Same as for the target trials.
Follow-up	Day 14 after date of vaccination or placebo will serve as the start of follow-up until the day of an outcome event, death, emigration or end of influenza season. Controls are censored if vaccinated.	Day 14 (time zero) after date of vaccination in each matched pair (index date) will serve as the start of follow-up until the day of an outcome event, death, emigration or end of influenza season (or latest possible date of data availability). Pairs are

		censored if controls are vaccinated.
Causal contrast of interest	
 • Intention to Treat – average effect of treatment assignment in trial population • Per-Protocol Effect – average effect among those who complied with their assigned treatment. 	
 • Modified Per- Protocol Effect – average effect among vaccinated (“do those who get the seasonal influenza vaccination benefit?”)
Statistical analysis	VE estimated as 1 - Risk Ratio at week 18 since index date using cumulative incidences from the Aalen-Johansen estimator.	Same as for the target trial. Week 18 subject to change according to data availability. Change will be made before any effectiveness results are estimated.

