ICU admission	Denmark	The National Patient Register and the Danish Microbiology Database. Defined as admission to an intensive care unit facility during hospitalization for influenza.
	Finland	Finnish Intensive Care Consortium's Quality Register for Intensive Care, National Care Register for Health Care and the National Infectious Diseases Register. Defined as admission to an intensive care unit facility during hospitalization for influenza.
	Sweden	The Swedish Patient Register, Quality Register for Intensive Care and the Register on surveillance of notifiable communicable diseases (SmiNet). Defined as admission to an intensive care unit facility during hospitalization for influenza.
All-cause mortality	Denmark	The Civil Registration Defined as a recording of death in the respective administrative demographic register (vital status is prospectively updated in these registers and also include information on the date of death).
	Finland	The Finnish Population Information System

		Defined as a recording of death in the respective administrative demographic register (vital status is prospectively updated in these registers and also include information on the date of death).
	Sweden	The Total Population Register, the Cause of Death Register Defined as a recording of death in the respective administrative demographic register (vital status is prospectively updated in these registers and also include information on the date of death).

Covariates

Determinants of vaccination and study outcomes are potential confounders in our studies. The richness of our health registers will allow us to provide detailed characterisations of health and disease status in individuals. We will be able to take the following confounders into account through exact matching: age (5-yr bins), sex, region of residency, and number of selected comorbidities (by 0, 1, 2, or ≥ 3 of chronic pulmonary disease, cardiovascular conditions, diabetes, autoimmunity-related conditions, cancer, and moderate-to-severe renal disease) as presented in Table 6.

Table 6. List of covariates

Variable	Country	Data source and details	Values/codes
Age	Denmark	The Civil Registration System. Recorded birth year. Age defined as 2024 minus birth year.	Categorical (for adjustment, using birth year): 5-year bins Binary (for stratification): $</\geq 75$ years

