9.7 Data analysis

Procedures

We will use a matched cohort design to evaluate the effectiveness of seasonal influenza vaccine in comparison with not receiving a seasonal influenza vaccine. Individuals who have received the vaccine will be matched on the day of vaccination with individuals who have not yet received the vaccine. Individuals will be matched on age (5-year bins), sex, region of residence, and selected comorbidities. The day the seasonal vaccine dose was administered within each matched pair will serve as the index date for both individuals. If individuals who were included as a matched non-vaccinated individual

(i.e., a reference individual) receive a vaccine later than the assigned index date, the pair will be right-censored on the day the non-vaccinated individual is vaccinated. In these cases, the non-vaccinated individuals will be allowed to potentially re-enter as vaccine recipients in a new matched pair on that given date.

Statistical analysis

We will follow individuals from day 14 after the index date (to ensure full immunisation) up until the day of an outcome event, death, emigration, or end of the study, whichever occurs first. Additionally, we will censor individuals with a positive PCR test for influenza in our follow-up period 14 and 30 days after the test (as a positive test will be part of the outcome definitions) for the influenza hospitalisation and death outcome analyses, respectively. We will right-censor matched pairs when the reference unvaccinated individual receives a vaccine during follow-up. Cumulative incidences will be estimated by the Aalen-Johansen estimator, and from these we will calculate the comparative VE as $1 - \text{risk ratio}$ at the start of week 18 (depending on data availability) since index date. The corresponding 95% CI will be calculated using the delta method. Country-specific estimates will be combined by random-effects meta-analyses implemented using the *mixmeta* package in R.

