9.8 Supplementary analyses and quality control

Confounding-by-indication and healthy vaccinee bias are critical methodological concerns in studies of influenza VE. (46). Confounding by indication would result in an underestimate of true effectiveness if individuals with comorbidities that increase the risk of the study outcome are more likely to get vaccinated. Healthy vaccinee bias occurs when healthy individuals are more likely to get vaccinated while the most frail and sick elderly with the highest risk of the study outcome are not vaccinated, especially at the end of life. In Table 8 below, we present the key possible confounders in studies of effectiveness and how they are likely to be associated with study exposures and outcomes.

Table 8. List of possible confounders in IVE studies

Possible Confounder	Influenza vaccination propensity	Influenza hospitalisation risk	All-Cause Mortality risk	Bias Direction for VE against	Bias direction for VE against

				influenza hospitalisation	all-cause mortality
Comorbidity	↑	↑	↑	Underestimate	Underestimate
High frailty	↓	↑	↑	Overestimate	Overestimate
Healthcare seeking	↑	↑	↓	Underestimate	Overestimate
Healthcare access	↑	↑	↓	Underestimate	Overestimate

The current state-of-the-art in observational vaccination effectiveness estimation is comprised mainly of two study approaches, the test-negative design and TTE. Both approaches seek to mitigate the impact of bias and confounding. Guilin and colleagues (47) evaluated the performance of the two approaches in the evaluation of Covid-19 VE estimation. In data with rich covariate information, they observed similar VE estimates from the two methods. In data with only a few covariates, the test-negative design tended to overestimate the VE, while the target trial emulation underestimated the VE.

To evaluate the potential for biases by healthcare-seeking behaviour or healthcare access, the TTE will be supplemented by a TND study. The TND study is only feasible in Denmark due to lack of test-negative results in Finland and Sweden. Moreover, supplementary analysis comprising of PERR, RDA, and Negative Control Outcomes Analyses will be conducted to allow for comparison and contextualisation of results. Moreover, to strengthen the robustness of findings, triangulation—integrating evidence from multiple analyses with different methodologies—can provide valuable insights into potential biases and enhance the interpretation of results.

Test-Negative Case Control design

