12. PLANS FOR DISSEMINATING AND COMMUNICATING STUDY RESULTS

Main results expected in the final study report:

- Baseline characteristics tables, including prior to matching and after matching, of two separate cohorts of 65+-year-olds (trial 1) and 18-64 years-of-age at increased risk (trial 2)
- Figures of cumulative incidence curves for vaccinated and unvaccinated, per country, outcome, brand and trial
- Brand-specific effectiveness estimates-tables with stratified analyses (age, sex, comorbidity, Covid-19 status, influenza vaccination history)
- Supplementary analyses results

We anticipate one manuscript, and findings will be reported to the general public by institutional press releases upon acceptance in academic peer-review journals or upon uploading to a pre-print server (if decided relevant to do so). The study protocol and study report deliverables will be made public in the HMA-EMA Catalogue of RWD studies when approved by EMA. We will adhere to the STROBE and ENCePP guidelines for the conduct of observational studies and for scientific independence and transparency.

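### Frailty, care seeking and care access are listed as key possible confounders, but nothing in the matching or the main analysis measures them; all-cause mortality is the most exposed outcome

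*Protocol*

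**What the plan says.** The matching set is described in three places of the Protocol:

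- Section 9.1, Table 1: "by age (5-yr bins), sex, region of residence, and presence of comorbidities".
- Section 9.3, Covariates: "We will be able to take the following confounders into account through exact matching", followed by "age (5-yr bins), sex, region of residency, and number of selected comorbidities", the count being 0, 1, 2 or at least 3 of six conditions.
- Section 9.7: "Individuals will be matched on age (5-year bins), sex, region of residence, and selected comorbidities".

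The wording for comorbidity differs, but none of the three includes a measure of frailty, prior admissions or care contacts, and neither does Table 6. For the main estimate, Section 9.7 says "Cumulative incidences will be estimated by the Aalen-Johansen estimator" and takes 1 minus the risk ratio from these curves. The Abstract speaks of adjusting for potential confounders, but Section 9.7 names nothing beyond the matching.

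Section 9.8 then says "In Table 8 below, we present the key possible confounders in studies of effectiveness". Table 8 has four rows: comorbidity, high frailty, healthcare seeking and healthcare access. The same section reports of an outside comparison: "In data with only a few covariates, the test-negative design tended to overestimate the VE, while the target trial emulation underestimated the VE". Section 12 promises strata that include "comorbidity, Covid-19 status, influenza vaccination history".

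**The concern.** Only one of the four Table 8 confounders has a variable in the design. Comorbidity cannot be assumed to stand in for frailty, because Table 8 lists them separately and gives them opposite bias directions for both outcomes it covers. The data for a partial remedy are already linked. Table 7 lists hospital contacts in the patient registers of Denmark (1995 on), Finland (1967 on) and Sweden (2017 on), and Table 6 uses the same registers for the 7-year comorbidity look-back.

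At stake is the interpretation of the main estimates, above all for all-cause mortality. Section 7 itself warns that this outcome can exaggerate vaccine benefit. Section 9.8 also says that an association with a negative control outcome would call for further adjustment or caution, but defines no variable with which to adjust.

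**Working it through.** **1. Table 8 against the design.**

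| Table 8 confounder | VE, influenza hospitalisation | VE, all-cause mortality | Direct measure in matching or Table 6 |
|---|---|---|---|
| Comorbidity | under | under | yes (count) |
| High frailty | over | over | none |
| Healthcare seeking | under | over | none |
| Healthcare access | under | over | none |

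For mortality, the one downward bias is matched on and the three upward ones are not. For hospitalisation, the three unmatched biases point in different directions.

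**2. Reach of the supplementary analyses (Section 9.8).**

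- PERR: influenza-related hospitalisation. The pre-period runs from 1 October 2024 to the index date and, by the plan's own account, may hold few events.
- Regression discontinuity: influenza-related hospitalisation, ages 60-69.
- Test-negative study: influenza infection, Denmark only.
- Negative control outcomes: run in the main design. They can reveal residual confounding but give no corrected mortality estimate.

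The first three do not address all-cause mortality.

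**3. Scale, by assumption only.** The plan gives no figure to reproduce. For one unmeasured binary confounder with prevalence pV in the vaccinated, pU in the unvaccinated and outcome risk ratio RR:

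B = [1 + pV(RR − 1)] / [1 + pU(RR − 1)], and observed VE = 1 − (1 − true VE) × B.

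All inputs below are assumptions; true VE is 40%.

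- Frailty, mild (10% vs 15%, RR 2): B = 1.10/1.15 = 0.957, VE reads 42.6%.
- Frailty, strong (10% vs 20%, RR 5): B = 1.40/1.80 = 0.778, VE reads 53.3%.
- Care seeking, mild (60% vs 50%, RR 1.25): B = 1.15/1.125 = 1.022, VE reads 38.7%.
- Care seeking, strong (80% vs 50%, RR 2): B = 1.80/1.50 = 1.20, VE reads 28.0%.

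If both act on hospitalisation and are taken as independent and multiplicative, the sign depends on the inputs. Start from frailty at 10% vs 20% with RR 3 (B = 1.20/1.40 = 0.857):

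- with care seeking 60% vs 40%, RR 1.5 (B = 1.30/1.20 = 1.083): product 0.929, VE reads 44.3%;
- with care seeking 80% vs 50%, RR 2 (B = 1.20): product 1.029, VE reads 38.3%.

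With a true VE of 0%, the frailty inputs alone give apparent VE from 4.3% (1 − 0.957) to 22.2% (1 − 0.778). For mortality, Table 8 has nothing unmatched that would offset this.

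**4. What a proxy would recover.** A sequential-matching simulation of 300,000 persons modelled frailty alone: prevalence 10%, vaccination hazard ratio 0.4 or 0.6, outcome hazard ratio 3, coverage 75.6% (the Danish figure for ages 65 and over in Section 9.5), true VE 0.40. Adding a binary proxy with 60% sensitivity and 90% specificity to the matching moved VE as follows:

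- from 0.537 to 0.517: (0.537 − 0.517)/(0.537 − 0.40) = 0.020/0.137 = 15%;
- from 0.485 to 0.470: 0.015/0.085 = 18%.

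**The case against.** The plan does not ignore the problem. Section 9.9 concedes that confounding can be substantial and sets out triangulation as the answer. A reader might infer that the supplementary analyses do no more than flag bias. The text does not support that: PERR yields an adjusted VE, the fuzzy regression discontinuity gives an instrument-based estimate, and the test-negative design reduces care-seeking bias by construction. This part of the objection stands for hospitalisation and infection. It does not reach all-cause mortality.

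A reader might also infer that the main VE is overstated by a definite amount. The documents do not support that either. Table 8 has opposing biases for hospitalisation, and the comparison cited in Section 9.8 found that emulation with few covariates underestimated VE.

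The proxy may not help every outcome. When care seeking was added to the simulation (prevalence 50%, vaccination hazard ratio 2, outcome hazard ratio 1.5 or 2, frailty vaccination hazard ratio 0.6), a true 40% read 40.5% and 36.0% under the plan's matching. With the proxy it read 39.4% and 34.8%, slightly further off. Other assumed settings moved it slightly closer. This is a reason to report results with and without the variable.

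Finally, Table 8 says possible confounders, universal tax-financed care and region matching limit differences in access, and age and comorbidity count partly track frailty. These points weaken the gap but do not close it.

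**Conclusion.** The gap is real and moderate in weight: three confounders that the plan itself names have no direct measure in the matching set, in Table 6 or in the main estimator. By the plan's own Table 8, the uncontrolled bias in all-cause mortality points upward, and no planned analysis corrects that estimate. For influenza hospitalisation the net direction is unknown and no single magnitude should be claimed; the figures above only show the range under assumed inputs.

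The documents also do not support the inference that adding one register variable would solve the problem. It removes a minority of the frailty bias, about 15-18% under the assumed accuracy. Admissions also reflect morbidity and care use, so they are a mixed proxy.

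**What to change.** Derive the number of hospital admissions in the 12 months before 1 October 2024 (0, 1, 2 or more) from the patient registers already linked in each country. Add it to the exact-matching set, or adjust for it within the matched cohort, for example by weighting the cumulative incidences. Fix the definition before any effectiveness result is estimated. Report VE and the negative control outcomes with and without it, and include all-cause mortality. State in Section 9.9 that this removes only part of the frailty confounding and that admissions also capture morbidity and care use.

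Previous-season influenza vaccination may be added as one sensitivity analysis only. An unvaccinated control who had a dose the season before has recently stopped, so the variable can bring in selection as well as remove it. Reconcile the Section 12 strata with the stratification list at the end of Section 9.3 (brand, age, sex) and with Table 6, which does not define vaccination history.

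The cost is one derived variable per country in the Common Data Model, a second run of the matched analysis and one sensitivity run. The downside is that some people in sparse cells will go unmatched; the documents do not allow their number to be estimated, so the matched share should be reported both ways.

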9. RESEARCH METHODS

9.1 Study design

We will take advantage of the unique nationwide register-data available to us, and construct country-specific cohorts with individual-level information on dates of vaccination and dates of effectiveness endpoints together with relevant covariate information. All Nordic residents are assigned a unique personal identifier at birth or immigration, enabling linkage between register data. Nordic countries have universal and tax-financed healthcare systems and reporting to national registers is mandatory, providing near-complete follow-up of all residents over time.

The study period will start on 1st October 2024 in the three countries. This study start date corresponds to the start of the seasonal influenza vaccination program in the three countries. The study period will end on the last date of data availability at time of analyses during spring 2025.

The study design will build on our previous work with Covid-19 vaccination effectiveness in the Nordic countries (19,20). We will utilize a cohort design in a target trial emulation (TTE) framework to estimate both relative and absolute effects. The evaluations in 65+-yr-olds and risk groups 18-64-yr-olds will be designed as two separate target trial emulations. Key components of the specification and emulation of the pragmatic target trials of the effectiveness of brand-specific seasonal IVE using Nordic nationwide register data are included below in Table 1.

Table 1. Target trial emulation framework

Protocol	Target Trial Specification	Target Trial Emulation
Eligibility criteria	
 • Individuals 65+-years-of-age (trial 1) • Individuals in risk groups 18-64-yr-of-age (trial 2) • Have a permanent residency in Denmark, Finland, or Sweden at start of study period 	Same as for the target trials.
Treatment strategies	Vaccination with any of the following influenza vaccines InfluvacTetra, VaxigripTetra, FludTetra, FluarixTetra or Efluelda Tetra, October 1, 2024 to January 31, 2025 vs vaccination with placebo in the same period.	Same as for the target trials except vaccination with placebo is replaced by no vaccination with any of the vaccines under study.

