9.2 Setting

Within Denmark, Finland, and Sweden, we will include all individuals aged 65 years and above, and individuals below 65 years of age at high risk of adverse influenza outcomes, who are known residents. We will analyse each target group in separate cohorts in each country.

Eligibility criteria for study inclusion are:

- 1) Individuals 65+-years-of-age (trial 1)
- 2) Individuals in risk groups 18-64-yrs-of-age (trial 2)
- 3) Have a known residency within the specific country at start of study period

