9.4 Data sources

All data sources are nationwide registers in native format. All study investigators have access to their country-specific data and can link data between registers for the purpose of our study. Given the near real-time availability of the data source, our analyses will provide timely evidence. Denmark and Finland will have full data availability for all variables (with no missing data; all the exposures, outcomes, or covariates are either present or not) during the study period and as reporting to national registers is mandatory/structurally implemented, this provides complete follow-up of all residents over time. Currently, Sweden has limited access to nationwide influenza vaccination data but will be able to provide data from four regions in Sweden with a combined population of 1,220,00 individuals. These include Uppsala Region (405,000), Jönköping Region (370,000), Blekinge Region (160,000), and Värmland Region (285,000).

Table 7. Overview of individual-level data sources in the three Nordic countries

Country	Data sources						
Denmark							
Title	Info	Type	Setting	Study availability	Update	Lag	Ref
The Danish Civil Registration System	The register provides the unique personal identifier for all permanent residents of Denmark that allows linkage between all Danish health care registers and civil registrations systems. In addition, it holds general demographic information such as birthdate and sex as well as continuously updated information and dates on historical addresses, immigration and emigration status, and death.	Register	Nationwide	1968- today	Daily	No lag	(24)

The Danish vaccination register	The register holds information on all vaccinations given in Denmark including information on vaccination date, brand, type, dose, and product batch number ever since November 15, 2015 (when reporting to the register became mandatory).	Register	Nationwide	2020 – today	Daily	No lag	(25)
The National patient registry	The register covers all hospital contacts/visits in Denmark with information on the duration of the contact/visit, department of admission and other hospital characteristics. Treating physician-assigned diagnoses have been registered according to ICD-10 codes since 1995.	Register	Nationwide	1995 - today	Daily	No lag	(26)

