While this method can yield robust causal insights under relatively few assumptions, it faces limitations related to sample size, adherence, and external validity. We will interpret RDA findings as part of our broader range of supplementary analyses, recognizing that they estimate a local average treatment effect for compliers in a narrow age interval that may not generalize to the whole population, and should be considered alongside the main cohort findings and other designs (e.g., TNCC, PERR). We will carefully evaluate the number of outcomes in this age range to ensure sufficient power. Even if RDA provides a rigorous causal estimate for the subset near 65, it may not reflect the effect in much older or younger individuals.

We will focus on individuals in an age band of 60-69 years, where the policy recommends seasonal influenza vaccination at age 65. We will extract data on vaccination status at the end of the study period or date of the outcome (yes/no), age (in years), and influenza-related hospitalizations for individuals aged 60-69. This subset ensures that the age threshold of 65 is central in the data, capturing individuals who are just below (60-64) and just above (65-69) the cutoff. Individuals below 65 who are at high-risk will be excluded since they were also offered vaccination. Influenza vaccination will be as assigned as the “treatment” variable. The “instrument” will be a binary indicator of whether an individual’s age is ≥ 65 (the vaccination policy cutoff). This instrument should, in theory, increase the probability of vaccination but is not assumed to directly affect health outcomes other than through vaccination.

The statistical analysis will be conducted using a fuzzy regression discontinuity model. The probability of being vaccinated can be estimated as a function of age relative to 65 (e.g., age - 65) and an indicator for crossing the 65-year threshold. The predicted probability of being vaccinated will then be used to estimate the effect on the outcome of interest (influenza-related hospitalisation). The package *rdrobust* in R can be used to conduct this analysis. We will also construct figures to visualize the discontinuity for outcome and for treatment.

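### The regression discontinuity analysis runs on whole-year age derived from birth year, which leaves ten values and a one-year gap below the cut-off and costs precision that recorded birth dates could save

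*Protocol*

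**What the plan says.** Table 6 in section 9.3 defines age for Denmark, Finland and Sweden as "Recorded birth year. Age defined as 2024 minus birth year". It gives two uses for the variable, matching or adjustment ("Categorical (for adjustment, using birth year): 5-year bins") and stratification at 75 years. The protocol contains no other definition of age.

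The RDA in section 9.8 restricts the data to ages 60-69: "We will extract data on vaccination status at the end of the study period or date of the outcome (yes/no), age (in years"). The running variable is given, as an example, as age minus 65. The instrument is an indicator of age 65 or more, described as the policy cut-off. The model is a fuzzy design, and the *rdrobust* package is named as a possible tool. Kernel and bandwidth are not stated.

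The eligibility list in section 9.2 reads "Individuals 65+-years-of-age (trial 1") and "Individuals in risk groups 18-64-yrs-of-age (trial 2"), with no date at which age is measured. The only reference date in that list belongs to residency: "Have a known residency within the specific country at start of study period". Section 9.1 says: "The study period will start on 1st October 2024 in the three countries".

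On what the registers hold, Table 7 in section 9.4 says of the Danish Civil Registration System that "it holds general demographic information such as birthdate and sex", and it lists date of birth for the Finnish Population Information System. It has no entry from which to tell whether Sweden has more than birth year.

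**The concern.** A regression discontinuity estimate compares people just below and just above a threshold. Section 9.8 rests on those two groups being alike. With age in whole years, the closest group below the cut-off is an entire birth year, and its fitted line must be extended one full year to reach 65. A local-polynomial method works best when many distinct values lie close to the threshold; here there are five on each side. The section itself names sample size as a limitation of the method and plans to check that there are enough outcomes, so precision given away here matters.

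A second, smaller matter comes from the same definition. Subtracting birth year from 2024 gives the age reached by 31 December 2024, while the study starts on 1 October. Since the eligibility criteria fix no date for age, a programmer would probably apply Table 6, and some people who are still 64 at study start would enter trial 1.

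**Working it through.** The protocol gives no figure on this point, so there is nothing to reproduce. Two checks follow.

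**1. Precision of the RDA with ten values of age**

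Inputs from the protocol: ages 60-69, whole years, x = age − 65. The upper side has x = 0, 1, 2, 3, 4 and the lower side x = −5, −4, −3, −2, −1.

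Assumptions: local linear fit with triangular kernel K = 1 − |x|/h; bandwidth h of 5, 4, 3 or 2 years; N persons at each year of age; equal outcome variance σ².

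On each side the fitted value at the cut-off is a weighted sum Σwᵢȳᵢ with variance (σ²/N)·Σwᵢ². With continuous age the weights at the boundary, for u = |x|/h, are 6(1 − u)(1 − 2u)/(hN). The integral of their square gives 4.8/(hN) per side, or 9.6/(hN) for both.

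Intercept weights with whole-year age:

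- h = 5, upper: 0.714, 0.343, 0.086, −0.057, −0.086, sum of squares 0.646. Lower (x = −5 to −1): 0, −0.3, −0.2, 0.3, 1.2, sum of squares 1.660.
- h = 4, upper: 0.8, 0.3, 0, −0.1, sum of squares 0.740. Lower (x = −3 to −1): −0.5, 0, 1.5, sum of squares 2.500.
- h = 3, upper: 0.9, 0.2, −0.1, sum of squares 0.860. Lower (x = −2, −1): −1, 2, sum of squares 5.000.
- h = 2: on the lower side only x = −1 has positive kernel weight, so the slope is not identified.

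| h | Whole years, Σw² | Continuous, 9.6/h | Ratio | SE ratio = √ratio |
|---|---|---|---|---|
| 5 | 0.646 + 1.660 = 2.306 | 1.92 | 1.20 | 1.10 |
| 4 | 0.740 + 2.500 = 3.240 | 2.40 | 1.35 | 1.16 |
| 3 | 0.860 + 5.000 = 5.860 | 3.20 | 1.83 | 1.35 |

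Most of the variance comes from the lower side, where the line is extended a full year. The same weights apply to the jump in outcome and the jump in uptake, so the factor carries over to their ratio when the size of the jumps is held fixed. This result does not depend on how any country invites people.

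**2. Age at eligibility**

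Everyone born in 1959 is coded 65. Under evenly spread births (an assumption), the number of the 365 birth dates not yet at the 65th birthday is:

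- 1 October 2024: 91/365 = 24.9%
- 15 October: 77/365 = 21.1%
- 15 November: 46/365 = 12.6%
- 31 December: 0%

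The 65+ population in section 9.5 is 1.211 + 1.315 + 0.280 = 2.806 million. If the age-65 birth year is 4% to 7% of it (an assumption), the share of trial 1 still 64 on 1 October is 0.249 × 4% = 1.0% to 0.249 × 7% = 1.7%, or about 28,000 to 49,000 people.

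**The case against.** The strongest defence is that the RDA is one of several supplementary analyses, to be read alongside the main cohort results, and that the package is named only as an option. A finer age variable could still be programmed. This limits the importance of the point. It does not remove it, because section 9.8 does write age in years and Table 6 supplies the only definition.

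A reader might go further and infer that a quarter of those coded 65 are put in the wrong trial and on the wrong side of the cut-off, so that both RDA jumps are diluted. The documents do not support that, for four reasons:

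- Table 6 is a covariate list and does not say that its age decides eligibility. A 64-year-old outside the risk groups would belong to neither trial, so "wrong trial" would fit only those at risk.
- Table 2 states the national age rules without saying whether 65 is counted by birthday or by calendar year. Under a calendar-year rule nobody is on the wrong side.
- The RDA takes vaccination status at the end of the study period or at the outcome. Everyone coded 65 has turned 65 by 31 December, inside the vaccination window that Table 1 runs to 31 January. Shares counted in October or November are therefore not shares never offered the vaccine, and no percentage dilution follows from them.
- The design is fuzzy. Even if the uptake jump were weakened by a full quarter, for example from 0.50 to 0.375, the ratio of the outcome jump to the uptake jump is unchanged under a homogeneous effect. The loss would be instrument strength, not a demonstrated bias.

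The obvious remedy, a cut-off at exact age 65 on 1 October, also fails under a birthday rule. People just below it become eligible within days, so uptake measured at the end of the study would show little jump there.

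**Conclusion.** The point holds as a loss of precision in the RDA. Ten whole-year values with a one-year gap on the lower side raise the standard error by about 10%, 16% and 35% at bandwidths 5, 4 and 3 compared with continuous age, and leave the lower slope unidentified at bandwidth 2. This rests on a triangular-kernel local linear fit, equal numbers per year of age, equal variance, and bandwidths chosen here because the protocol gives none.

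The missing reference date for age at eligibility is a real but minor gap. It touches about 25% of one birth year on 1 October, roughly 1-2% of trial 1 under the assumed 4-7% share. The same age rule applies to vaccinated people and their matched controls, and no bias in vaccine effectiveness is shown. Misassignment at the cut-off, and any percentage dilution of the RDA, cannot be asserted from the documents.

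**What to change.** In the RDA, replace whole-year age with date or month of birth as the running variable wherever the register holds it; by Table 7, Denmark and Finland do. State each country's invitation rule and place the cut-off at the birth date that the rule implies:

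- If people are invited by calendar year, the boundary lies between 31 December 1959 and 1 January 1960.
- If they are invited by birthday, allow for those who turn 65 during the vaccination window, for example by leaving out those birth dates (a donut). For the window in Table 1 these are 2 October 1959 to 31 January 1960. Do not cut at exact age 65 on 1 October.

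Where only birth year is available, report the RDA as an analysis with a discrete running variable and say so. Separately, add to section 9.2 the date at which age is measured for trial 1 and trial 2.

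The cost is one extra derived variable in the Common Data Model, plus a small loss of sample if the donut is used. It removes 122 birth dates out of 3,653 in the birth years 1955-1964 (3.3%). They are the ones nearest the cut-off, so the precision cost is somewhat larger than that share, but the 122-day gap is still well short of a full year.
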